12.1. Statistical Hypotheses

State the formal and testable null and alternative hypotheses for primary and key secondary endpoints, specifying the type of comparison (e.g., superiority, equivalence or non-inferiority, dose response) and time period for which each endpoint will be analyzed.

We hypothesize that compared with those in the control group (usual care), the subjects in the intervention group (modified Sodium Watcher Program-Hypertension) will show;

- Hypothesis 1: a trend for reduced urinary sodium excretion
- Hypothesis 2: a trend for improved BP control

12.2. Sample Size Determination

Include number of participants to recruit, screen, and enroll to have adequate power to test the key hypotheses for the study. Provide all information needed to validate your calculations and judge the feasibility of enrolling and following the necessary number of participants.

Given the pilot nature of the study, we will recruit 40 participants and conduct a stratified randomized clinical trial. Specifically, 40 subjects will be recruited, and block randomized to either an intervention or a control group in a 1:1 ratio. Per power analysis, the study will be underpowered; therefore, quantitative outcomes will be interpreted only as feasibility and pilot data. A sample size of 40 subjects will give us adequate sample size to provide meaningful confidence intervals for our estimates of feasibility and preliminary effects. With this overall sample size, we expect to have sufficient diversity of input on the intervention components to plan refinements prior to testing in a larger intervention trial.

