10.1. Measures to Minimize Bias: Randomization and Blinding

This section should contain a description of randomization and blinding procedures (if applicable to the study design). It should include a description or a table that describes how study participants will be assigned to study groups, without being so specific that blinding or randomization might be compromised. Plans for the maintenance of trial randomization codes and appropriate blinding for the study should be discussed. The timing and procedures for planned and unplanned breaking of randomization codes should be included. Include a statement regarding when unblinding may occur and who may unblind. Provide the criteria for breaking the study blind or participant code. Discuss the circumstances in which the blind would be broken for an individual or for all participants (e.g., for serious adverse events (SAEs)). Indicate to whom the intentional and unintentional breaking of the blind should be reported.

- Subjects (N=40) will be randomized in a 1:1 ratio into two groups using a computer program that generates random numbers to receive modified Sodium Watchers intervention. Everyone will receive a baseline and end of study visits.
- Subjects randomized to (Group 1) intervention group (IG) will be asked to follow the modified Sodium Watchers Program intervention along with goal setting for low salt foods. Each subject will be registered to assign a unique ID in the Connected Health Platform developed by the Center on Smart and Connected Health Technologies at UT Health Science Center San Antonio (UTHSCSA) and each account from the individuals' wireless and wearable devices (Fitbit and BP monitor) will be connected to his or her unique ID through this platform. Subjects will be instructed to log their activities in real-time, including food intake and in-home BP monitoring using Fitbit and accompanied mobile app and BP monitor. Through the Connected Health Platform, the Fitbit app and BP monitor will transmit the data of the intervention group to the research team. The PI will remotely track user engagement and will call participants if they fail to measure any behavior for 3 days using "Sync function" or subscribing to "Alerts" which will alert us when a user has an inactive or invalid status.

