10.3. Permitted Concomitant Therapy

This section should be consistent with the medication restrictions in the inclusion/exclusion criteria previously listed. Describe how allowed concomitant therapy might affect the outcome (e.g., drug-drug interaction, direct effects on the study endpoints).

Participants in both groups won't be restricted from their previous antihypertensive medications. All relevant data, including medication usage and other forms of therapy, will be considered when conducting data analysis wherever necessary to avoid or minimize its effects on study endpoints.

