12.4. Statistical Analyses

Include analysis of primary efficacy endpoints, secondary endpoints, safety analyses, and any planned interim analyses

Data analysis will be performed with SAS (Cary, NC) version 9.4 and R (Vienna, Austria) version and 3.6+. After verifying the normality of distribution of the continuous variables, the mean and standard deviations will be calculated. If data are not normally distributed, log transformation will be conducted. All analyses will also be conducted after controlling for age, gender, and BMI.

Specific Aim 1: Using pre-test data, random forest will be applied to identify associations between 48 amino metabolites, BP phenotypes (including SBP or DBP), and 24-hour urinary excretion to predict the classification of study subjects and will be achieved by R program. For urinary metabolites nominated by the random forest analysis, generalized linear model (GLM) will further be performed to generate p values and false discovery rates (FDR) to correct for testing multiple urinary metabolites using the Benjamini-Hochberg procedure.

Specific Aim 2a: Using both pre and post-test data, feasibility will be assessed by measuring: 1) % subjects who come to the 8-week follow-up; 2) number of education sessions attended online (intervention group); 3) % days that subject log his/her meals using mobile dietary app; and, 4) % days that subject log in-home BP using BP monitor device. The preliminary effect of SRD on the outcome variables will be tested by using a repeated measures analysis of variance (RM-ANOVA) with one between-subjects factor (intervention and control) and one within-subject factor (pre-test and post-test).

Specific Aim 2b: We estimate that 20 participants/group will provide sufficient data for estimating intervention effects on metabolomic profiling and reduction of urinary sodium level and BP. The estimated effect size will be used for sample size justification and power analysis for a future larger study.

Specific Aim 3: Using pre-test data, analysis of targeted genotyping will be conducted by the R program. A moderator analysis will be used to determine whether the relationship between urine metabolites or sodium intake and BP depends on the SS candidate gene (GNAI2 SNPs).

All testing will be two-sided and p<0.05 or FDR < 10% will be considered as significant.

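### Section 12.2 calls the trial stratified but names no factor, and the 12.4 arm comparison has no term for one outside age, gender and BMI; if such a factor predicts change, the intervals are conservatively wide

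*Combined protocol and SAP*

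**What the plan says.** - **Allocation, 12.2.** The plan is to "conduct a stratified randomized clinical trial. Specifically, 40 subjects will be recruited, and block randomized to either an intervention or a control group", with equal allocation. No stratification factor, number of strata or block size is given there or elsewhere.
- **Allocation, 10.1.** "Subjects (N=40) will be randomized in a 1:1 ratio into two groups using a computer program that generates random numbers". Strata and blocks are not mentioned.
- **Arm comparison, 12.4 (Aim 2a).** The model is described as "repeated measures analysis of variance (RM-ANOVA) with one between-subjects factor (intervention and control) and one within-subject factor (pre-test and post-test".
- **Adjustment, 12.4.** "All analyses will also be conducted after controlling for age, gender, and BMI". No stratum term appears.
- **Use of the result.** Section 12.2 says that 40 subjects is an "adequate sample size to provide meaningful confidence intervals for our estimates of feasibility and preliminary effects", and that "quantitative outcomes will be interpreted only as feasibility and pilot data". For Aim 2b, 12.4 adds: "The estimated effect size will be used for sample size justification and power analysis for a future larger study".

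**The concern.** Stratified blocks balance the arms on the stratification factor, so the estimated arm difference varies less from trial to trial than under simple randomisation. A model without the factor leaves the between-stratum variation in its error term. It therefore reports a standard error larger than the true one whenever the factor predicts the quantity being compared.

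In a two-arm, two-time repeated measures ANOVA, the group-by-time test is the comparison of pre-to-post changes. What matters is thus whether the stratum predicts change, not whether it predicts level.

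A conservative p-value matters little in a pilot. At stake are the two quantities that this pilot is meant to hand on: the confidence intervals, which 12.2 uses to justify N = 40, and the Aim 2b effect size, which is to feed the next trial's sample size.

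**Working it through.** **Inputs from the documents.** N = 40 (12.2); 20 per arm (12.4, Aim 2b), and 2 × 20 = 40 agrees; two-sided 5% (12.4); arm and time factors with age, gender and BMI (12.4). No SD, effect size, power figure or target interval width is stated, so N = 40 cannot be re-derived.

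**Context.** The unadjusted 95% half-width for a difference in mean change is t(0.975, 38) × √(2/20) = 2.024 × 0.316 = 0.64 SD of change. Power at 20 per arm (normal approximation) is about 35% for 0.5 SD and 72% for 0.8 SD. This fits the statement in 12.2 that the study is underpowered.

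**Assumptions.** Two strata, permuted blocks of 4 within stratum, and a share R² of the variance of change explained by the stratum. The documents give none of these, so R² is ranged from 0 to 20%.

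**Formula.** Ignoring degrees of freedom, the width without the stratum divided by the width with it is 1/√(1 − R²).

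**Simulation.** Change = b × stratum + effect × arm + N(0,1), with b set to give R². N = 40, 50:50 strata, and three independent covariates standing in for age, gender and BMI. Least squares with and without the stratum; 20,000 runs for type I error and 10,000 for power at an assumed 0.8 SD.

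| R² (assumed) | 1/√(1 − R²) | Simulated width ratio | Type I error, omitted / included | Power, omitted / included |
|---|---|---|---|---|
| 0% | 1.000 | 0.998 | 5.1% / 5.0% | 66.0% / 66.0% |
| 5% | 1.026 | 1.025 | 4.5% / 5.0% | 63.6% / 65.6% |
| 10% | 1.054 | 1.055 | 4.0% / 5.0% | 60.6% / 64.8% |
| 20% | 1.118 | 1.122 | 2.9% / 4.9% | 56.1% / 65.5% |

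With 30:70 strata, type I error without the stratum is 5.2%, 4.5%, 4.1% and 3.0%. With 20% dropout, the width ratios are 0.992, 1.019, 1.049 and 1.115.

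**Separate check without covariates (20,000 runs each).** Coverage of the nominal 95% interval without the stratum is 94.8%, 95.5%, 96.0% and 97.0% at the same four shares. With the stratum it stays between 94.7% and 95.0%.

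**Aim 2b.** Standardising by the unadjusted SD multiplies the effect by √(1 − R²), which is 0.975, 0.949 and 0.894 at 5%, 10% and 20%. A future sample size scales as 1/(1 − R²), which is 1.053, 1.111 and 1.250. It would be about 5%, 11% or 25% too large, but only for a trial that adjusts for the same strata.

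**Form of the term.** A stratum main effect is constant over time and cancels from the pre-to-post change. In one simulated pre/post data set, the group-by-time standard error was 0.3494 with no stratum term, 0.3494 with a stratum main effect, and 0.3272 with stratum-by-time.

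**Cost if the stratum predicts nothing.** The R² = 0 ratios are 0.998 (two strata), 0.992 (two strata, 20% dropout) and 0.988 (four strata of 10). Including the term therefore widens the interval by 0.2%, 0.8% and 1.2%.

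**The case against.** The loss depends on several conditions that the documents do not settle. Strata must actually be used; since 12.2 goes straight on to describe blocks, the word may be a slip. The factor must lie outside age, gender and BMI, because otherwise the adjusted analysis would largely account for it. It must predict change and not only level. For Aim 2b, the later trial must also adjust for the same strata. All of this stands, and it is why the conclusion is conditional.

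The size is also small beside the pilot's own uncertainty. On a half-width of 0.64 SD, widening by 2.5%, 5.5% or 12% adds about 0.02, 0.04 or 0.08 SD. An observed effect of 0.8 SD would have an interval of roughly 0.16 to 1.44. At 80% power, with n per arm = 2 × (1.96 + 0.84)²/d² ≈ 15.7/d², that implies a future trial of anywhere from about 8 to about 613 per arm. An overstatement of 5% to 25% is minor against that range, and it errs towards a larger trial. This stands too and sets the severity.

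It does not remove the point. Followed as written, with any other stratum, the plan leaves a randomisation factor out of the analysis, and the remedy costs almost nothing.

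**Conclusion.** The point holds conditionally and is minor. If strata outside age, gender and BMI are used and they predict change, the arm-comparison intervals are about 2.5%, 5.5% or 12% too wide at assumed shares of 5%, 10% or 20%. The Aim 2b standardised effect is then slightly small for a future trial that adjusts for the same strata. If the stratum does not predict change, nothing is lost. Two strata, blocks of 4 and every share are assumptions. Severity is limited because 12.2 confines quantitative outcomes to pilot use.

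A reader might infer more in four places, which the documents do not support:

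- **Inflated false positives.** The error runs the other way: type I error falls and coverage rises.
- **A contradiction between 10.1 and 12.2.** Computer-generated random numbers are compatible with stratified blocks. Section 10.1 is less detailed, not inconsistent.
- **A broken commitment on medication.** Section 10.3 says medication use "will be considered when conducting data analysis wherever necessary to avoid or minimize its effects on study endpoints". That is discretionary and promises no covariate. In simulations under assumed models, a yes/no medication term in the metabolite and BP analyses cut false positives in some cases (15% to 5%) and raised them in another (11% to 21%). A with-and-without sensitivity analysis is optional.
- **Cluster randomisation.** The box ticked in 5.2 conflicts with the individual allocation in 10.1 and 12.2, but this is a clerical matter.

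**What to change.** In 12.4, include the stratification factor or factors actually used in every arm comparison. Enter them as stratum-by-time in the repeated measures ANOVA, or as a covariate in a change-score or baseline-adjusted model. A stratum main effect alone would leave the group-by-time interval unchanged. Name the factors in 12.2 so that the model can be checked against the allocation.

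If no stratification is intended, delete the word stratified from 12.2. That is an equally valid repair, and 12.4 then needs no change on this account.

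The cost is protocol wording and one model component (more coefficients if there are several strata), with about 0.2% to 1.2% in interval width if the stratum turns out to predict nothing.

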12.3. Populations for Analyses

Clearly identify and describe the analysis datasets (e.g., which participants will be included in each).

For data analysis, we will include data from study participants who have completed baseline and follow-up survey, and anthropometric and biomarker measurements.

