11.2. Continued Follow-up Discontinuation of Study Intervention

Describe efforts that will be made to continue follow-up of participants who discontinue the study intervention, but remain in the study for follow-up, especially for safety and efficacy study endpoints (if applicable). Reasonable efforts must be made to undertake protocol-specified safety follow-up procedures to capture adverse events (AE), serious adverse events (SAE), and unanticipated problems involving risks to subjects or others (UPIRSOs).

This is expected to be a minimum risk study with dietary interventions. All participants will be allowed to discontinue the study at any time. Despite study intervention termination, it is optional for participants to continue use mobile devices to monitor their health status.

12. Statistical Considerations

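### Section 12.3 applies one completer-only analysis set to every aim, which distorts the feasibility measures, leaves Aim 2 open to bias and discards usable baseline data from Aims 1 and 3

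*Combined protocol and SAP*

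**What the plan says.** Section 12.3 answers the template's request for analysis datasets with one sentence, covering data analysis in general: "we will include data from study participants who have completed baseline and follow-up survey, and anthropometric and biomarker measurements". No other set is defined, and section 12.4 assigns no aim a different population. Neither section says how missing values are handled.

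Section 12.4 then lists analyses with different data needs:

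- Aim 2a, feasibility: the first measure is the percentage of "subjects who come to the 8-week follow-up". The others are online sessions attended (intervention group) and the percentages of days with meals and with home blood pressure logged.
- Aim 2a, preliminary effect: a pre/post repeated-measures ANOVA comparing the two groups.
- Aim 2b: "We estimate that 20 participants/group will provide sufficient data for estimating intervention effects". The resulting effect size is to be used to plan a larger study.
- Aim 1: "Using pre-test data, random forest will be applied to identify associations".
- Aim 3: "Using pre-test data, analysis of targeted genotyping will be conducted by the R program".

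On follow-up, section 10.1 says "Everyone will receive a baseline and end of study visits". Section 11.2, on people who stop the intervention, says only that "it is optional for participants to continue use mobile devices to monitor their health status".

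**The concern.** A set defined by completing follow-up cannot serve all these purposes. Retention cannot be measured in a group selected for having been retained. Engagement measured only in those who stayed will tend to look better than engagement among everyone offered the programme.

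For Aim 2, excluding randomised participants because of something that happens after randomisation weakens the protection that randomisation gives. Outcome-related loss is plausible from the documents themselves. Section 10.2 anticipates attrition. Section 11.1 stops the intervention when worrying blood pressure readings appear, and blood pressure is an outcome. Section 11.2 does not say that week-8 measurements are still sought after that. The completion criteria are also joined by *and*, so a missing week-8 urine sample could remove a participant's blood pressure data as well.

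Aims 1 and 3 need no follow-up data, so the rule removes valid records for no analytic reason.

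Feasibility and an effect size for the next trial are the main outputs of this pilot, and section 12.2 justifies the 40 participants by the confidence intervals they will give for both.

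**Working it through.** **The plan's own figure.** 20 per group × 2 groups = 40 (sections 12.2 and 12.4). Nothing more can be reproduced, because no dropout rate, effect size, SD, power or interval width is given. Losses of 10%, 20% and 30%, equal in both arms, are therefore assumed.

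**1. Retention.** With all randomised as denominator it is completers/40. With section 12.3 applied literally it is completers/completers. Intervals are exact (Clopper-Pearson) 95%.

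| Assumed loss | All 40 as denominator | Section 12.3 literally |
|---|---|---|
| 10% | 36/40 = 90% (76% to 97%) | 36/36 = 100% (90% to 100%) |
| 20% | 32/40 = 80% (64% to 91%) | 32/32 = 100% (89% to 100%) |
| 30% | 28/40 = 70% (53% to 83%) | 28/28 = 100% (88% to 100%) |

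At 20% loss, the literal interval excludes the true 80%.

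**2. Sessions.** Assumptions: eight weekly sessions (section 7 gives eight weeks of sessions but no count), completers attend 7, dropouts attend 2. With k dropouts among the 20 in the intervention group, the mean over all randomised to it is ((20 − k) × 7 + k × 2)/20:

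- k = 2: 130/20 = 6.5
- k = 4: 120/20 = 6.0
- k = 6: 110/20 = 5.5

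The completer set reports 7.0 each time.

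**3. Logging.** Assumptions: logging on 80% of days while in the study, and dropouts stop on day 14 of 56. A completer logs 0.8 × 56 = 44.8 days and a dropout 0.8 × 14 = 11.2 days, which is 20% of scheduled days. With L lost, the share of all scheduled days is ((40 − L) × 44.8 + L × 11.2)/(40 × 56):

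- L = 4: 1657.6/2240 = 74%
- L = 8: 1523.2/2240 = 68%
- L = 12: 1388.8/2240 = 62%

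The completer set reports 80% each time. If dropouts instead log between 10% and 40% of scheduled days, the all-randomised figure at 20% loss is 66% to 72%.

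**4. Aims 1 and 3.** The number analysed falls from 40 to 36, 32 or 28. Interval width for a regression coefficient scales roughly with √(40/n): √(40/36) = 1.05, √(40/32) = 1.12, √(40/28) = 1.20.

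**5. Aim 2.** If a share d of one arm is lost and those lost differ from that arm's completers by k SD, the completer mean for that arm is off by d × k. The documents support no value for k, so no bias is calculated; it is zero when k = 0. Precision can be stated: the 95% half-width for a difference in means is t × √(2/n), with t on 2n − 2 degrees of freedom. This gives 0.64 SD at 20 per arm and 0.72 SD at 16 per arm.

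**The case against.** The strongest reply is that 100% retention is the least plausible reading. A percentage attending week 8 means something only if the denominator includes people who did not attend, and sections 10.1 and 12.2 use the word subjects for all 40. A specific measure in section 12.4 would normally override a general sentence in section 12.3. That is fair: the retention figure shows a conflict to be reconciled rather than a result the team is likely to publish. The same rescue is not available for sessions and logging, which can be computed in completers without looking absurd.

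Section 12.4 does separate pre-test from pre- and post-test data. Those phrases name time points, though, not participants, and so do not exempt Aims 1 and 3 from the rule.

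Section 12.3 requires completed measurements, not a completed intervention. Someone who stops attending sessions but comes at week 8 stays in the set, and that person's low engagement counts. The engagement examples assume that those who disengage also miss week 8; with partial overlap the overstatement is smaller. This stands.

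For Aim 2, repeated-measures ANOVA with two time points drops unpaired participants in any case, and a mixed model with one post-baseline visit recovers little from people who have only a baseline value. No analysis set restores 20 week-8 values per group once people are lost. These points also stand. They mean that rewording section 12.3 alone is not enough for Aim 2, and that obtaining the week-8 data matters more than the choice of model.

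Finally, section 12.2 limits interpretation to feasibility and pilot data. That tempers the severity, but these are the quantities the rule affects.

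**Conclusion.** The concern holds and should be fixed before analysis. Section 12.3 is the only rule on who is analysed, and following it as written gives worse answers than the data would allow.

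At assumed losses of 10% to 30%, retention of 90% to 70% would read as 100% on the literal reading. Mean sessions would be overstated by 0.5 to 1.5 and logging by 6 to 18 percentage points, if dropouts disengage early and also miss week 8. Intervals in Aims 1 and 3 would widen by about 5% to 20%. Aim 2 becomes a completer comparison, open to bias if loss is related to outcome and differs by arm; no size is claimed. Its planned 20 per group is reached only with zero loss.

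The dropout and engagement inputs are assumptions. With no dropout and complete measurements, none of these effects arises.

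**What to change.** Replace section 12.3 with a set for each aim:

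- **Feasibility:** all randomised as denominator. For sessions, all randomised to the intervention; for logging, all scheduled days from randomisation.
- **Aim 2:** all randomised, analysed as assigned, using every available value of each outcome. A likelihood-based mixed model, valid under missing at random, is one option. Keep completers as a sensitivity analysis. State that this does not remove bias from loss driven by unobserved outcomes, and report loss and its reasons by arm.
- **Aims 1 and 3:** everyone with the baseline data that the analysis needs.

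Align the Aim 2a wording in section 12.4, since the ANOVA it names uses only complete pairs. Add a sentence to section 11.2 saying that the week-8 measurements are sought whether or not the intervention was stopped.

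The cost is rewording and slightly more analysis work. No participants or visits are added, because section 10.1 already plans an end-of-study visit for everyone.
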